2.3.3 Training for those providing interventions A and B

The clinical and technical team of the SIMAP project will train the clinicians working in the participating ARUs of the project in the clinical trial and use of SIMAP. Two training sessions of 30 minutes each, delivered in groups, are planned. In the first of these sessions, an explanation will be provided about the intervention, as well as essential principles regarding how pictograms would facilitate users' understanding of the instructions. The second session will involve the direct application of these pictograms to simulated patients under the guidance of the SIMAP design team.

2.3.4 Follow-up (procedure developed in the same way for both Group A and B)

The follow-up will be conducted according to what is shown in Table I.

Table I: Follow up procedure beginning (t0), 7 days (t1), 30 days (t2) and 60 days (t3)

		Study Period						
		CESFAM Professional	Clinical professional hired by the project (recruiter)	Clinical professional hired by the project (follow-up)	t0	t1	t2	t3
Recruitment	Application of Eligibility Criteria	X			X			
	Informed Consent Signature		X		X			
	Bio-sociodemographic Profile		X		X			
	Charlson Index		X		X			
	ACT test		X		X			
Intervention A	Delivery of instructions with Pictograms	X	X		X			
Intervention B	Delivery of informative brochure		X		X			
Follow-up	ACT test			X		X	X	X
	Inhalation			X		X	X	X

	Technique Adherence Guideline							
--	-------------------------------------	--	--	--	--	--	--	--

3. Data & Statistical Analysis Plan

3.1. Outcomes

The primary outcome of the study consists of the difference in disease control level 60 days after the start of the study, as assessed by the ACT questionnaire. As co-primary outcomes, the same score difference observed at 7 and 30 days after the intervention has been established, as well as adherence to the recommendations provided by the healthcare team regarding the correct inhalation technique for bronchodilators and the use of inhalation chambers within the same time frames. Secondary outcomes of the study include the recognition of the function of bronchodilators. To check adherence to the correct application of the inhalation technique, the project clinician will conduct an assessment of the correct use of the prescribed inhalation therapy according to a checklist developed 10 months after the start of the project. The checklist was developed following the recommendations of national clinical guidelines, the Spanish Association of Pediatrics in Primary Care, and a study conducted by Santo Tomás University on inhalation techniques in asthmatic patients (Manríquez et al., 2015).ris

Additionally, secondary outcomes will include the occurrence of urgent care visits, hospitalizations related to the disease, and the need to escalate bronchodilator therapy as per GINA guidelines at 60 days. Information regarding these secondary outcomes will be extracted from the individual medical records of each patient, as well as during the final follow-up interview when the ACT questionnaire is administered.

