3.2. Sample Size

In this stage, we will be working with new patients entering the ARU. Based on the actual population size of adult patients with bronchial asthma recorded from 2019 to 2021 in the participating centers of the project, we have considered a minimum sample size of 48 patients, with a 10% margin of error and a 95% confidence level. We anticipate recruiting this sample within a period of no more than 6 months from the entry of the first patient. The sample calculation takes into account the years during which the COVID-19 social and health crisis occurred. Additionally, due to the lack of previous literature on the evaluation of pictograms for asthma control, it is not feasible to calculate a sample size based on the effect size to be achieved. Ideally, we aim for a homogeneous sample according to the a priori population of entries for each participating center. However, in case of recruitment difficulties at any health center, the sample will be obtained based on the center with the highest availability of patient entries that meet the selection criteria. Considering the measurement of the primary and co-primary outcomes, we plan to randomize a minimum of 48 patients for Stage 2 of the clinical validation of SIMAP.

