3.4. Analysis Strategy

The statistician hired by the project will conduct the data analysis for Stage 2 of the study. Descriptive analysis will initially involve means, standard deviation, absolute and relative frequencies. For inferential analysis, either Student's t-tests or Mann-Whitney tests will be employed to compare means based on the distribution and variances of the obtained data. The Fisher's Exact Test will be used for evaluating qualitative variables.

The primary outcome will be assessed concerning the difference in mean scores observed in bronchial asthma control questionnaires (ACT) between groups at each time point through a profile analysis. The secondary outcome will be evaluated based on the proportion of patients adhering to recommendations regarding the correct use of bronchodilators between both groups. Any intra-group comparisons of qualitative data will be conducted using the ANCOVA or Kruskal-Wallis statistic, depending on the distribution of quantitative data.

All analyses will be carried out by a statistician unaware of the treatment assignment of the participants. Outcomes will be analyzed on an intention-to-treat basis (intervention or control group). In the event of an imbalance in the characteristics of the groups established by the randomization process, potential adjustments to the models will be made. Any model generated will consider the presence of potential interactions between independent variables during its design. Maximum likelihood principles will be ensured based on residual analysis.

To preserve the intention-to-treat principles, missing data will be handled using multiple imputation techniques. All analyses will be performed by a masked statistician using R Project software.

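### Adherence is co-primary in Section 3.1 but secondary in Section 3.4, and the plan gives no alpha, testing order or success rule for its primary-level outcomes

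*Combined protocol and SAP*

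**What the plan says.** Section 3.1 names one primary outcome: "The primary outcome of the study consists of the difference in disease control level 60 days after the start of the study", measured by the ACT. It goes on: "As co-primary outcomes, the same score difference observed at 7 and 30 days after the intervention has been established, as well as adherence" to the team's advice on inhalation technique and "the use of inhalation chambers within the same time frames". Technique is judged by an "assessment of the correct use of the prescribed inhalation therapy according to a checklist". The secondary outcomes in Section 3.1 are recognition of what the bronchodilators do, urgent visits, hospitalizations and therapy escalation. Adherence is not among them.

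Section 3.2 keeps the co-primary label: "Considering the measurement of the primary and co-primary outcomes, we plan to randomize a minimum of 48 patients".

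Section 3.4 assesses the primary outcome as ACT mean differences "between groups at each time point through a profile analysis". It then says: "The secondary outcome will be evaluated based on the proportion of patients adhering to recommendations regarding the correct use of bronchodilators between both groups". For categorical data, Fisher's "Exact Test will be used for evaluating qualitative variables".

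Table I (Section 2.3.4) schedules the inhalation-technique adherence checklist at days 7, 30 and 60.

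**The concern.** The rank of an outcome decides what a positive result may be called. Suppose day-60 ACT shows no difference and adherence does. Section 3.1 would support reporting a primary-level success, and Section 3.4 would support reporting a secondary finding beside a null primary. Because both texts are current, the choice could be made once the results are known. It would bear on the main conclusion, since Section 1.2.2 lists therapeutic adherence among the effects to be validated.

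A single label would still not settle what counts as success. With several outcomes at primary level and no rule for combining them, the trial's false-positive rate cannot be stated.

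**Working it through.** **1. Are the two adherence outcomes the same?**

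- *Technique:* the Section 3.1 checklist judges correct use of the prescribed inhaled therapy, and Section 3.4 speaks of correct use of bronchodilators. Nothing on the Section 3.1 secondary list concerns adherence, so no other listed outcome fits. The inference is strong.
- *Chamber use:* co-primary in Section 3.1 and not mentioned in Section 3.4. A change of rank is not shown.
- If Section 3.4 did mean something else, the co-primary adherence outcome would have only the generic Fisher test as its analysis, and an undefined secondary outcome would have appeared. The sections would still need reconciling.

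**2. Does the sample size supply a rule?** The plan's figure is 48, from a 10% margin of error and 95% confidence. With an assumed proportion of 0.5, n0 = 1.96² × 0.5 × 0.5 / 0.10² = 96.04. With the finite-population correction n = n0·N/(n0 + N − 1), N = 93 gives 47.50 and N = 94 gives 47.75, both 48 when rounded up. The population size is not stated, so 48 is plausible but cannot be confirmed. Either way this is a survey-precision calculation. Its 95% is not a test alpha, and it sets no power for any outcome.

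**3. How many primary-level comparisons are there?** ACT contributes three visits. Adherence may be compared at one visit (Section 3.4 gives one proportion and no visit), at two (the time frames in Section 3.1 follow the mention of days 7 and 30) or at three (Table I). Technique and chamber use may be one endpoint or two. Adherence therefore adds k = 1, 2, 3, 4 or 6 comparisons, for totals of 4, 5, 6, 7 or 9.

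**4. False-positive rate under each possible rule.** Assumed, because the plan does not say: two-sided 5% per test and 24 per arm.

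- Only day-60 ACT counts: 5%.
- All must succeed: no inflation.
- Any one success counts: the exact size of Fisher's test at 24 versus 24 is 2.94% at 50% adherence, its maximum. With separate ACT t-tests at each visit, the ceiling under independence is 1 − 0.95³ × (1 − 0.0294)^k. With one 5% omnibus ACT test it is 1 − 0.95 × (1 − 0.0294)^k.

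| Comparisons | k | Separate ACT tests | One omnibus ACT test |
|---|---|---|---|
| 4 | 1 | 16.8% | 7.8% |
| 5 | 2 | 19.2% | 10.5% |
| 6 | 3 | 21.6% | 13.1% |
| 7 | 4 | 23.9% | 15.7% |
| 9 | 6 | 28.3% | 20.6% |

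Positive correlation lowers these. So do extreme adherence rates: at 10% or 90% adherence the Fisher size is 1.7%, and the nine-comparison ceiling with separate ACT tests falls to 22.6%.

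**5. Power cost of controlling the error rate.** With 24 per arm and 80% power (noncentral t), the detectable ACT difference is 0.83 SD at alpha 0.05, 0.92 SD at 0.025 (two outcomes) and 1.04 SD at 0.05/6 (six outcomes, first Holm step). If two outcomes must both succeed and each has 80% power, joint power is 0.80² = 64% when they are independent and about 71% at a correlation of 0.7.

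**The case against.** The strongest reply is that Section 3.1 does name one primary outcome with its day, and that the singular primary outcome in Section 3.4 can be read with that definition. Analysing ACT at every visit is also what Section 3.1 requires, since days 7 and 30 are co-primary there. This stands. A reader might infer that Section 3.4 replaces day 60 with all visits, or that early ACT is ranked inconsistently. The documents do not support either: no section ranks day-7 or day-30 ACT as secondary. For early ACT the gap is the missing success rule alone.

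A reader might also infer that the plan inflates the type I error. It does not show that. Two of the three possible rules keep the error at or below 5%, and the inflated figures rest on an assumed any-one-success rule, per-test alpha and adherence rate. Nor does Section 3.4 say which profile-analysis hypothesis is tested.

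It could be argued that co-primary conventionally means that all must succeed. The plan never says so, and setting one primary apart from the co-primaries fits that reading poorly. Masking the statistician does not help either, because the open choice is how to rank a result once it is known. The small sample and the lack of an effect-size basis explain modest aims, but the plan still names primary outcomes and sets out to validate an effect.

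**Conclusion.** The point holds for the rank of adherence and for the missing decision rule. The label conflict is plain on the text for technique, given the inference that correct bronchodilator use in Section 3.4 is what the Section 3.1 checklist measures. It is not established for chamber use. The absence of an alpha, a testing order and a success rule applies to every primary-level outcome, early ACT included.

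The error rate is undetermined rather than shown to be inflated. The 17% to 28% range is a ceiling for one reading only: any one success suffices, ACT is t-tested separately at each visit, adherence is 50% and outcomes are independent. The case for correction rests on the contradiction and the missing rule, not on those percentages.

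**What to change.** Give adherence the same rank in Sections 3.1 and 3.4, and state one decision rule in Section 3.4. Two forms would work, and the choice is the sponsor's.

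1. **Single primary.** Name the between-group ACT contrast at day 60, within the profile analysis, as the only primary comparison at two-sided 5%. Label ACT at days 7 and 30 and adherence as secondary in both sections. *Cost:* the objectives in Section 1.2 name understanding, retention and adherence but not asthma control, so no outcome named there would be tested at primary level.
2. **Adherence kept at primary level.** Correct Section 3.4 to match Section 3.1 and prespecify a fixed testing order, a Holm adjustment, or a rule that all must succeed. One named adherence comparison at one visit beside day-60 ACT would keep the loss smallest. *Cost:* power. If two outcomes split alpha, the detectable ACT difference rises from 0.83 to 0.92 SD. More outcomes cost more.

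Under either form, state the visit or visits at which adherence is compared and whether technique and chamber use are one endpoint or two. The change is to wording only, needs no extra patients or data, and should be made before outcome data are seen.

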3.2. Sample Size

In this stage, we will be working with new patients entering the ARU. Based on the actual population size of adult patients with bronchial asthma recorded from 2019 to 2021 in the participating centers of the project, we have considered a minimum sample size of 48 patients, with a 10% margin of error and a 95% confidence level. We anticipate recruiting this sample within a period of no more than 6 months from the entry of the first patient. The sample calculation takes into account the years during which the COVID-19 social and health crisis occurred. Additionally, due to the lack of previous literature on the evaluation of pictograms for asthma control, it is not feasible to calculate a sample size based on the effect size to be achieved. Ideally, we aim for a homogeneous sample according to the a priori population of entries for each participating center. However, in case of recruitment difficulties at any health center, the sample will be obtained based on the center with the highest availability of patient entries that meet the selection criteria. Considering the measurement of the primary and co-primary outcomes, we plan to randomize a minimum of 48 patients for Stage 2 of the clinical validation of SIMAP.

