2.3.2 Assignment to intervention group A or control group B

- Patients will be randomized using a permuted block method to receive one of two possible intervention strategies A or B.
- The permuted block technique aims to ensure a periodic balance in the number of subjects assigned to each intervention or control group (Molina et al., 2015).
- The random assignment sequence will be generated by technical staff of the project with the support of a statistician.

Intervention Group A: This intervention involves utilizing a pictogram system named SIMAP (Automatic Association System of Medical Instructions to Pictograms), which was developed during the initial phase of the study. In essence, SIMAP comprises a series of pictograms intended to enhance the understanding of medical instructions provided by the healthcare team regarding asthma management. The pictograms will be designed by a panel of experts, as detailed in the previous sections of the project, and validated among adult patients consulting in the same population where this study will be implemented. The designed pictograms are specifically tailored to certain elements within the management of bronchial asthma.

This intervention entails furnishing the patient with the instruction sheet given by the clinical staff of the CESFAM as part of their care, but supplemented with pictograms (automatically generated by SIMAP). The provided instructions include images supporting guidance for recognizing bronchodilators, indicating their method of use (daily dose, usage schedule, or as needed), specifications of bronchodilator families with their functions (disease-controlling and symptom-relieving drugs), inhalation technique of bronchodilators, and the use of an inhalation chamber in the process.

The pictograms will be administered by the clinical professional of the CESFAM designated by the Director or by the clinical professional hired by the project (recruiter). This depends on the care process of the CESFAM participating in this study and the availability of hours of the clinical professional of the CESFAM designated by the Director to support the project.

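### The 10% margin of error at 95% confidence used to justify 48 patients does not describe the A-versus-B comparison; with 24 per arm the day-60 ACT half-width is about 0.58 SD

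*Combined protocol and SAP*

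**What the plan says.** Section 3.2 (Sample Size) gives one quantitative basis for the trial's size. It starts from a recorded population, "Based on the actual population size of adult patients with bronchial asthma recorded from 2019 to 2021 in the participating centers of the project", and continues: "we have considered a minimum sample size of 48 patients, with a 10% margin of error and a 95% confidence level". It gives neither the size of that population nor the formula or the proportion assumed. It states that, without earlier literature, a calculation from an effect size was not feasible. It closes by tying the number to the outcomes: "Considering the measurement of the primary and co-primary outcomes, we plan to randomize a minimum of 48 patients".

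The rest of the plan describes a two-arm comparison:

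- Section 2.3.2: "Patients will be randomized using a permuted block method to receive one of two possible intervention strategies A or B". No allocation ratio is given.
- Section 3.1: the primary outcome is "the difference in disease control level 60 days after the start of the study, as assessed by the ACT questionnaire". ACT at 7 and 30 days and adherence to inhalation technique are co-primary.
- Section 3.4: the primary outcome is assessed as the "difference in mean scores observed in bronchial asthma control questionnaires (ACT) between groups at each time point through a profile analysis", and adherence is compared as a proportion between the groups.

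No dropout allowance is stated. Section 3.4 says only that "missing data will be handled using multiple imputation techniques".

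**The concern.** A margin of error in per cent, combined with a population size and a confidence level, is what one uses to estimate a single prevalence in one group. It contains no second arm, standard deviation, target difference or power. The population cited is a historical register, whereas section 3.2 itself says "In this stage, we will be working with new patients entering the ARU".

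Because the section ends by linking 48 to the primary and co-primary outcomes, and 10%/95% is the only precision figure offered, a reader can take it as the precision of those comparisons. The trial would then look much more informative than it is. The practical risk is at interpretation: a non-significant ACT result could be read as evidence of no benefit when a moderate effect has not been excluded.

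**Working it through.** **Inputs from the documents.** Total 48 (a minimum), margin 0.10, confidence 95% (section 3.2); two groups in permuted blocks (2.3.2); difference in mean ACT and difference in adherence proportions (3.1, 3.4).

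**Assumptions, because the plan is silent.** 1:1 allocation, so 24 per arm; two-sided alpha 0.05 per outcome without multiplicity adjustment; ACT results in SD units because no SD is given.

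**1. Reproducing 48.** The one-proportion formula is n0 = 1.96² p(1 − p)/0.10².

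- p = 0.5, no correction: n0 = 3.8416 × 0.25/0.01 = 96.04, so 97, not 48.
- p = 0.5 with finite-population correction, n = n0·N/(n0 + N − 1): setting n = 48 gives N = 48 × 95.04/48.04 ≈ 95.
- No correction: solving 3.8416·p(1 − p)/0.01 = 48 gives p ≈ 0.146.
- Other pairs also fit, for example p = 0.3 with N ≈ 117 and p = 0.2 with N ≈ 216.

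So 48 is compatible with a one-group survey formula, but this cannot be confirmed without N and p. In all of these versions the 10% refers to the 48 patients pooled.

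**2. What the same formula gives for one arm.** Keep the correction, with N = 95 and p = 0.5:

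- All 48 pooled: 1.96 × √[(0.25/48) × (47/94)] = 0.100.
- One arm of 24: 1.96 × √[(0.25/24) × (71/94)] = 0.174.

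The margin is already lost within a single arm, before any comparison is made.

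**3. Day-60 ACT difference.** Half-width = t(0.975, df) × √(1/n₁ + 1/n₂) in SD units. For 24 per arm: 2.013 × √(2/24) = 2.013 × 0.2887 = 0.581 SD. Detectable differences and power come from the noncentral t distribution.

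| Scenario | Half-width (SD) | Difference at 80% power (SD) | Power at 0.5 SD |
|---|---|---|---|
| 24/24, complete data | 0.58 | 0.83 | 40% |
| 22/22 evaluable (assumed loss) | 0.61 | 0.86 | 37% |
| 19/19 evaluable (assumed loss) | 0.66 | 0.93 | 32% |
| 32/16 (2:1 allocation) | 0.62 | 0.88 | 36% |
| 24/24, baseline-adjusted, assumed r = 0.5 | 0.50 | 0.72 | 50% |

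The adjusted row uses variance factor 1 − 0.5² = 0.75 and 45 degrees of freedom.

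In ACT points, 0.581 SD is 1.7, 2.3 or 2.9 points at assumed SDs of 3, 4 or 5; 0.826 SD is 2.5, 3.3 or 4.1 points.

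**4. Adherence at one visit.** Half-width of the difference = 1.96 × √[2p(1 − p)/24], by normal approximation:

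| p in both arms | Half-width (points) |
|---|---|
| 0.10 | ±17 |
| 0.15 | ±20 |
| 0.30 | ±26 |
| 0.50 | ±28 |

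These are 1.7 to 2.8 times the stated 10 points. Newcombe intervals average about ±19 points at p = 0.1 and ±26 at p = 0.5. At p = 0.5 a ±10-point half-width would need 1.96² × 0.5/0.01 = 192.1, so 193 per arm.

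**The case against.** The strongest reply is that section 3.2 is candid. It says an effect-size calculation was not feasible, so no one is told that the trial is powered. Its closing sentence does not repeat the 10% or claim it for a between-arm difference, and 48 is called a minimum, so the figures above describe the floor. This is fair as far as it goes. It explains why there is no target effect, and the review does not dispute that. It does not make a one-group margin apply to the comparison, and precision in SD units needs no prior effect estimate.

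Other points stand in part:

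- The survey formula is inferred, and several pairs of N and p fit. The conclusion is the same for each.
- Section 3.4 leaves the test open (t-test or Mann-Whitney, a profile analysis, possible adjustment), so an unadjusted t-test is a reference case. Adjustment at r = 0.5 improves the half-width only to 0.50 SD; a stronger correlation would improve it further.
- For adherence, the half-width depends on the interval method, and section 3.4 plans Fisher's exact test. By either method computed here it is well above 10 points. Section 3.1 makes adherence co-primary while section 3.4 evaluates it as secondary; the precision is the same under either label.
- The attrition range, ACT SDs, correlation and 2:1 ratio are not in the documents. They are assumptions and are shown as ranges.

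The correction alters no patient's treatment and no data collected, so one could call it minor. But it concerns the only quantitative justification for the trial's size.

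**Conclusion.** The concern holds. The 10% margin at 95% confidence is not a property of any A-versus-B estimate in this trial, and it should not stand as the justification for 48 in relation to the primary and co-primary outcomes. With 24 per arm, two-sided alpha 0.05, an unadjusted t-test and complete data, the primary comparison has a half-width of 0.58 SD and 80% power at 0.83 SD. Across the loss, allocation and adjustment scenarios shown, the half-width runs from 0.50 to 0.66 SD. Only the size of the gap depends on these assumptions; that the margin belongs to a different quantity does not. The number 48 itself, as a feasible minimum, is not in dispute. This must be corrected before the plan is relied on.

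**What to change.** In section 3.2, keep 48 as a feasibility-based minimum and keep the statement that no target effect was available. Remove the 10%/95% phrase as justification for the comparison. State the allocation ratio actually used, and add wording such as the following, recalculated if the ratio is not 1:1:

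> Assuming 1:1 allocation (24 per arm), two-sided alpha 0.05 per outcome, an unadjusted two-sample t-test and complete data, 48 patients give a 95% CI half-width of about 0.58 SD for the day-60 ACT difference and 80% power for a true difference of about 0.83 SD. With 22 to 19 evaluable patients per arm these become 0.61–0.66 SD and 0.86–0.93 SD. Adjustment for baseline ACT could narrow them. For a difference in adherence proportions at one visit, the half-width with 24 per arm (normal approximation) is about ±17 to ±28 percentage points for proportions from 0.1 to 0.5. A non-significant result does not rule out smaller effects.

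If section 3.4 is settled on a different primary model, the ACT sentence should be matched to it.

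Cost: protocol and SAP wording only. The stated precision becomes less favourable. No extra patients are needed, and design and data collection do not change.
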